Include any age, language, gender, or race-related inclusion/exclusion criteria and provide a justification for the use of these criteria. If applicable, please provide a rationale for your choice in sample size and/or sample size calculation.

If you are conducting research in languages other than English, translated versions of the participant-facing research materials (e.g., informed consent, recruitment materials, measures, etc.) must be submitted for review along with the [Certificate of Translation form](#).

(Max ¼ page)

Participants/Sample Size: Female patients who have been recommended for minimally invasive gynecologic surgery. A total of 100 patients will be enrolled in this study at UCR Women's Health Clinic. Statistical power. To rationalize the consideration of statistical power, we determined that 100 subjects will be needed to predict a difference of improvement in patient's post-operative experience ranges 20% or greater.

Inclusion criteria:

- Age 18 – 65 years old
- Surgery with UCR Gynecology physician
- Laparoscopic/robotic surgery
- Same day discharge after surgery
- Can read a survey in English
- Female

Exclusion Criteria:

- Receiving postoperative chemotherapy in the 6-week postoperative period
- Minors under the age of 18

- Postoperative overnight stay
- Laparotomy (open surgery)
- Pregnancy

16. Special Populations

a) Will any participants/subjects be specifically recruited from the following categories listed below (check all that apply):

Under the age of 18

Prisoners, probationers, or parolees

Pregnant women, fetuses, or neonates

Other characteristics that may cause them to be considered 'vulnerable' (e.g., cognitively impaired, educationally/economically disadvantaged, patients, students, staff, history of distrust, etc). Describe:

b) If YES, please justify the use of the above populations, and detailing what additional safeguards will be included in the study to protect the rights and welfare of the subjects and will there be direct benefits. If NO, skip to the next question.

(Max ¼ page)

17. Recruitment: Describe the mode of communication and how participants will be approached. Any recruitment materials, e-mails, & scripts must be submitted for review as appendices.

If you are recruiting participants through a subject pool (e.g., Psychology Department subject pool), please refer to the UCR [Policy on the Use of Subject Pools in Human Subjects Research](#).

(Max ¼ page)

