All patients undergoing surgery will be asked to participate in the study. No PHI would be needed for randomization. Patients will be approached in the office setting once they have decided to proceed with surgical management. The surgeon, fellow or clinical research team will approach the participants. Please see the roster for a list of participants involved in the consenting process. They will be handed a "study info" pamphlet that describes the purpose, methods and involvement of the study. The participants will then be scheduled for a preoperative visit. All patients who decide to have surgery are scheduled for a preoperative visit in our office, and patients will be reminded of the study and asked if they want to participate. If consent is granted, the patient will be randomized to receive the preoperative instructions verbally or via an instructional video." The surgeon, fellows and clinical research team are part of the research team.

18. Compensation: Will participants be compensated for their time? Describe the methods, amount and schedule for payment. What will happen to compensation if participants chose to withdraw? If no compensation is being offered, please justify why.

(Max ¼ page)

There is no patient compensation. The study involves no cost to subject participation.

19. Reimbursement: Will participants personally incur any expenses as a result of participation (e.g., fuel, missed work)? If no reimbursement is being offered, please justify why.

(Max ¼ page)

Patients will not incur any expenses as a result of participation.

20. Procedures

a) Describe how human participants will be involved in the research. If there is to be an intervention or interaction with the participants, describe what the researcher and participants will do, who will conduct the procedures, where and when the procedures will take place, how frequently, for how long, what equipment will be used, etc.

(Max ½ page)

Patients will be invited to participate in the study by principal investigator or co-investigator or designated study personnel (Appendix Project Roster) when the patient will be undergoing a minimally invasive gynecologic surgery.

Patient will be consenting in the clinic and randomization will take place the same day patient consent is obtained.

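### Same-day discharge, overnight stay and open surgery are worded as actual status although patients are randomised before surgery, and nothing keeps unplanned cases in the analysis (minor)

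*Combined protocol and SAP*

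**What the plan says.** Section 15 (Participant Population) describes the population as "Female patients who have been recommended for minimally invasive gynecologic surgery". Its inclusion list has "Same day discharge after surgery" and laparoscopic or robotic surgery. Its exclusion list has "Postoperative overnight stay" and open surgery (laparotomy). No entry carries a word such as planned, scheduled or expected.

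Section 20a (Procedures) says that "randomization will take place the same day patient consent is obtained", and Section 23a (Consent Process) repeats this. Consent is sought in the clinic, when surgery is being scheduled (Section 23a) or at the preoperative visit (Section 17). Section 20a has the video group watch the video at the clinic on the day of surgery, before the operation.

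On numbers, Section 15 says both "A total of 100 patients will be enrolled in this study" and "we determined that 100 subjects will be needed to predict a difference of improvement".

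No section says whether a randomised patient who unexpectedly stays overnight, or whose operation is converted to open surgery, is kept, removed, replaced or analysed. The text contains no definition of an analysis population and no intention-to-treat rule.

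**The concern.** Eligibility criteria should depend only on what is known when a patient is randomised. As worded, these depend on what happens during and after the operation. Someone cleaning the data could find a randomised patient who meets a listed exclusion and delete her in good faith, with her arm already known.

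Two things are at stake. First, the groups compared might no longer be the groups randomised. Overnight stay plausibly goes with pain, tablet use and satisfaction, which the two-week survey measures. Section 12 asks whether better understanding from the video leads to faster recovery, so a different overnight rate by arm cannot be ruled out. Second, the number needed and the number enrolled are both 100, so each patient removed takes the analysis below the plan's own requirement.

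**Working it through.** **1. Order of events.** Consent and randomisation fall on the same day (Sections 20a and 23a). The video follows on the day of surgery (Section 20a), then the operation, then discharge or an overnight stay. Allocation precedes actual discharge status and actual surgical approach under every reading of the consent timing.

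**2. What the text says about unplanned cases.** The nearest statements are:
- Section 20a: complications are treated as usual. This concerns care, not analysis.
- Section 20a: both groups are scheduled for the two-week visit, with no condition on discharge.
- Section 25: data are discarded if the patient wishes to withdraw. Overnight stay is not mentioned.
- Section 29b: loss to follow-up is the only problem anticipated.

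None orders removal, and none forbids it.

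**3. The plan's figure.** The 100 cannot be reproduced, because Section 15 gives no alpha, power, SD or control rate and does not say on what scale the 20% is measured. The point does not depend on it. From the plan alone: 100 enrolled − 100 needed = 0 margin.

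**4. Would the question arise?** The documents give no overnight rate. At an assumed 2%, the chance of at least one case in 100 patients is 1 − 0.98^100 = 87%. At 5% it is 1 − 0.95^100 = 99.4%.

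**5. Power if patients are removed.** Assumptions: 1:1 allocation, two-sided alpha 0.05, 80% power at N = 100, and removed patients no different from the rest. Power = Φ(2.80 × √(N/100) − 1.96).

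| Removed | N analysed | Power |
|---|---|---|
| 0% | 100 | 80% |
| 5% | 95 | 78% |
| 10% | 90 | 76% |
| 15% | 85 | 73% |

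These are upper figures for the loss. If overnight patients score differently, keeping them widens the variance. Take 10% overnight in both arms, 1 point worse, SD 1.0 within each group:
- Keeping everyone: variance 1.0 + 0.10 × 0.90 × 1² = 1.09; SE = √(2 × 1.09/50) = 0.209.
- Same-day only: SE = √(2 × 1.0/45) = 0.211.
- Power falls from 80% to Φ(2.80 × 0.209/0.211 − 1.96), about 79%.

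**6. Shift in the treatment difference (illustration only).** Suppose overnight patients score g points worse than same-day patients in both arms, with overnight rates p_c (control) and p_v (video). The video-minus-control difference in same-day patients, less the same difference in all randomised patients, is −g × (p_c − p_v).
- Equal rates, or g = 0: shift 0.
- 12% v 8%, g = 0.5: 0.5 × 0.04 = 0.02 points.
- 15% v 5%, g = 1.0: 1.0 × 0.10 = 0.10 points on the 1–5 scale.
- If g is measured against the whole-arm mean instead, the last case gives 0.15/0.85 − 0.05/0.95 = 0.12 points.

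The sign reverses if the rates are swapped. No rate or gap here comes from the documents.

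**The case against.** The strongest reply is that planned status is simply what the criteria mean. They sit in an entry list that can only be applied at consent, the population is defined by a recommendation for surgery, both groups go to follow-up unconditionally, and the only data removal described is for patients who choose to withdraw. This largely stands, and it is why the point is small. But a planned reading settles only who enters the trial. It does not say who is analysed, and no other rule in the text fills the gap.

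Several stronger readings are tempting but not supported:
- **The plan excludes patients after randomisation.** No section orders this. It follows only from applying the list literally to actual status.
- **The video changes the overnight rate.** Section 12 raises faster recovery as a research question. The documents do not link a video of about 10 minutes to same-day discharge. A contrast such as 15% v 5% is an assumption, and part of the resulting shift is a change of target (effect in same-day patients v effect in all randomised) rather than pure bias.
- **A chance imbalance in overnight stays would bias the result.** It causes no bias on average and is not evidence of harm here.
- **The zero margin is caused by this wording.** It applies equally to any attrition, including the loss to follow-up that the plan anticipates, and the 100 is not itself a verified threshold.
- **Power would suffer badly.** The working shows a small loss, and a smaller one if overnight patients really do worse.

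**Conclusion.** The concern holds as a minor point. Three criteria are stated as actual status although allocation comes first, and the handling of randomised patients who depart from them is not stated. The wording allows removal on a recovery-related event after randomisation; it does not require it.

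The effect on the treatment comparison is of unknown size and may be zero. It needs removal to take place, overnight rates to differ by arm, and overnight patients to score differently. For conversion to open surgery, no arm-related route is claimed; the issue there is only the unstated handling. The power loss with 10% removed is between about 1 and 4 percentage points from an assumed 80%, depending on how overnight patients score. All rates, gaps, SDs, the 1:1 allocation and the starting power are assumptions. Only the order of events and the 100 needed v 100 enrolled come from the plan.

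**What to change.** - In Section 15, word the criteria as status planned at randomisation: planned same-day discharge (no planned overnight stay) and planned laparoscopic or robotic approach (no planned laparotomy).
- Add one analysis sentence: all randomised patients with outcome data who have not withdrawn are analysed in their assigned arm, including those with an unplanned overnight stay or a conversion to open surgery.
- Report overnight stays and conversions by arm from the medical records already being reviewed. Section 20b already lists surgical procedure and intraoperative complications. Overnight stay is not listed and should be added as one item.
- Use the same-day-discharge subset only as a sensitivity analysis.

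The cost is a wording change, one sentence and one recorded item, with no extra patients or visits. The downside is slightly more outcome variability from keeping unplanned overnight stays and conversions. In the example above, the larger number retained offsets this.

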 Yes	 X No (If Yes, please contact PRO for a separate review)
------------------------------	-------------------------------------------------------------------------------------------------------------

9. Additional Reviews

a) Has the research project received a scholarly, scientific, or peer review prior to this submission (this may involve a review by a funder, faculty supervisor, or a departmental committee):

 Yes, specify: [name], [name]
 No (NB: IRB recommends a prior scholarly review for studies that are more than minimal risk)
 Pending, specify:

b) Will this research require review by any of the following (check all that apply):

None – UCR IRB is the only approval required

Other (e.g., UCR or non-UCR entities – such as UC [Reliance](#) Registry, [SMART IRB](#) or another IRB)

Specify entity and status of review:

UCR Institutional Biosafety Committee ([IBC](#)): Research using biohazardous materials including any human-derived materials such as blood, body secretions, and tissues, primary and established cell lines

UCR Stem Cell Oversight Committee ([SCRO](#)): Research using human pluripotent cells

UCR Institutional Animal Care and Use Committee ([IACUC](#)): Research using vertebrae animals

II – Study Summary

10. Abstract (suitable for a lay audience)

(Max ¼ page)

In this study we will evaluate the impact of a pre-operative instructional video for patients undergoing a minimally invasive gynecologic surgery. The video will educate patients to understand what to expect and how to take care of themselves after the procedure. The effectiveness of the video will be evaluated via a questionnaire to see if patient's who watched the video had better recovery outcomes, greater understanding, and less anxiety when compared to the group of patients who did not watch the pre-operative video.

11. What is the scholarly rationale for this study?

(Max ½ page)

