Minimally invasive gynecologic procedures are considered lower risk than highly invasive surgeries, however, any surgical procedure can be a source of anxiety and fear for patients (1). Studies show that pre-operative videos for various procedures can reduce patient anxiety and increase patient satisfaction (2). Pre-operative video education was shown to increase understanding of their operation and lessen feelings of uncertainty in patients who received a lumbar puncture. Another study found that interaction between the patient and physician in addition to a video was more effective than an interview alone or interview with written material when measuring patient satisfaction and the amount of information gained (3). This is important because pre-operative anxiety and confusion can lead to poorer outcomes and recovery post- surgery. We want to add to this collection of data and see if the same results appear when pre-operative audio-visual material is shown to patients before they undergo their scheduled minimally invasive gynecologic surgery.

12. What are the study hypotheses or research questions?

(Max ¼ page)

1. Will the patients who watch the pre-operative will show decreased anxiety and uncertainty about their procedure when compared to the control group?
2. Will increased understanding of the information shared in the video result in less pain medication usage, less ambiguity and thus increased compliance with post-operative care instructions, and quicker recovery?

III – Study Design and Methodology

13. Study Timelines

Estimated start date for involvement of participants: Upon IRB Approval

Estimated completion date for the involvement of participants: 6 –9 months.

14. Location of Research

a) Where will this study take place? If it's a collaborative study, provide details regarding other site(s). If there is an online component, provide details.

(Max ¼ page)

UCR Women's Health Clinic. Letter of access from [name] attached

b) If research is taking place within a community or an organization, describe how access will be obtained.

Are there any special considerations for obtaining consent? Access letters may be requested from the community or organization. Sample Access Letter template can be found on the [ORI Resources page](#). Attach any relevant supporting documentation as appendices.

(Max ¼ page)

N/A

15. Participant Population: Please describe the participants/subjects. List the inclusion/exclusion criteria.

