The study group of patients will come to the clinic on the day of their surgery and be asked to watch the informational video about what to expect after their procedure and instructions on how to recover. They will be encouraged to ask their provider any follow up questions. [The instructional video is approximately 10 minutes long.](#)

The control group of patients will receive the standard patient education in place before the procedure and will also be able to ask to follow up questions from their provider.

Both groups will be scheduled for their routine two-week postoperative visit. Some patients schedule a telehealth postoperative visit, if a telehealth visit is scheduled, then a text or email will be sent. If the patient comes in person, the option of filling out the questionnaire in paper form, receive text or email to complete the survey. [The survey will take approximately 10 minutes to complete.](#)

Our primary outcomes will be patient level of satisfaction with the education they received prior to surgery and its impact on post-operative care which will be measured by the standardized likert scale (1 to 5 scale where 1 = strongly disagree and 5= strongly agree). The survey will include the following objective and subjective measures: Tylenol tablets used (over two weeks), Ibuprofen tablets used (over two weeks), pain scale (1 to 5 scale where 1 = none and 5= very severe). Additional information will be collected from the patient's medical records (ie. office visit notes, telephone encounters, hospital laboratory results, pain medication refill requests). Patients should continue any medication regimen as instructed by their physician up to the day of surgery. Patients will be treated for complications as they would have been treated otherwise. Study duration period will be approximately six months.

b) If you are using a dataset, please list out the variables you will be accessing. If you are using the Psychology Subject Pool, please list out the pre-screening data you will be collecting on your participants.

(Max ½ page)

[Chart review data: Age, Ethnicity, BMI, Smoking status, Narcotic use before surgery, Pain levels before surgery, Preop hemoglobin, Indication for surgery, Surgical procedure, Diagnosis, Presence of other pain disorders such as Interstitial cystitis, fibromyalgia, Intraoperative complications,](#)

[and Intraoperative blood loss.](#)

REDCAP Database will be used for the following purposes:

- Data collection

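### Hypothesis 2 asks about pain medication use, but the survey measures listed are Tylenol and ibuprofen counts with no opioid count, and the pre-operative pain and narcotic data have no stated use (minor; secondary outcome only)

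*Combined protocol and SAP*

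**What the plan says.** Section 12 (hypotheses), question 2, asks whether better understanding results in "less pain medication usage", along with better compliance and quicker recovery. Section 20a makes this a non-primary outcome: "Our primary outcomes will be patient level of satisfaction with the education they received prior to surgery" and its effect on post-operative care, rated 1 to 5.

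The survey measures that section 20a lists for pain and medication are "Tylenol tablets used (over two weeks), Ibuprofen tablets used (over two weeks), pain scale", the last scored 1 to 5. The same section adds medical-record sources: "office visit notes, telephone encounters, hospital laboratory results, pain medication refill requests". No drug class is given for the refill requests.

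Section 20b lists chart variables that include "Narcotic use before surgery, Pain levels before surgery". The text available assigns them no adjustment, stratification or subgroup role. It states no analysis model for any outcome.

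None of the five exclusions in section 15 concerns narcotic use; the first, for instance, is "Receiving postoperative chemotherapy in the 6-week postoperative period". Section 10 says that "The effectiveness of the video will be evaluated via a questionnaire" and names recovery, understanding and anxiety as its targets, so the list in section 20a is not the whole survey.

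**The concern.** The question covers pain medication as a whole, while the listed counts cover two named drugs. The plan treats narcotics as relevant before surgery, since it records them from the chart and does not exclude users, but it lists no matching count afterwards.

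If opioids are taken and the video shifts patients between opioids and the two listed drugs, the counts can stay flat or rise while total use falls. A fall in the counts alone could also be reported as less pain medication when it is not.

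The second part is smaller. The two baseline variables closest to the pain and medication outcomes will be collected, but nothing says they will be used. That gives up some precision and leaves the choice of covariates open until the data are seen.

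**Working it through.** **The plan's own figure.** The only effect size is "a difference of improvement in patient's post-operative experience ranges 20% or greater", attached to 100 patients. It is not tied to pain medication. No alpha, power, base rate or SD is given, so the 100 cannot be reproduced. Assuming 1:1 allocation, two-sided 5% and 80% power, 75% against 95% needs 98 in total and 40% against 60% needs 194. Neither concerns tablet counts.

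**Assumed inputs.** The documents supply none of these:
- 50 per arm (100 split 1:1).
- Opioid share of control-arm doses s = 0, 10, 20 or 30%.
- The video halves opioid doses (h = 0.5).
- A fraction f of the dropped doses is replaced one-for-one by Tylenol or ibuprofen.
- Coefficient of variation (CV) of the counts 0.5 to 0.8.

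**Direction of the listed counts.** Change in total doses = −s·h·(1−f). Change in listed counts = s·h·f/(1−s). For s = 0.2 and f = 0.5, the total changes by −0.2×0.5×0.5 = −5%, and the counts by 0.2×0.5×0.5/0.8 = +6.25%.

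| Replaced (f) | Total, s = 0 / 10 / 20 / 30% | Listed counts |
|---|---|---|
| none | 0 / −5 / −10 / −15% | 0% throughout |
| half | 0 / −2.5 / −5 / −7.5% | 0 / +2.8 / +6.3 / +10.7% |
| all | 0% throughout | 0 / +5.6 / +12.5 / +21.4% |

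With s = 0 nothing is lost.

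**How often this would show.** SE of the relative difference = CV×√(2/50), which is 0.10 at CV 0.5 and 0.16 at CV 0.8. In the half-replaced row, the chance that the count estimate points upward is Φ(change/SE). For s = 10 / 20 / 30% this is 61 / 73 / 86% at CV 0.5 and 57 / 65 / 75% at CV 0.8. The chance of a significant rise (noncentral t, 98 df) is 5 / 9 / 18% and 4 / 6 / 10%. The likely harm is a missed change, not a significant reversal.

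**Refill requests as a substitute.** The 95% half-width for a difference in proportions is 1.96×√(2p(1−p)/50). For p = 5 / 10 / 20% it is 8.5 / 11.8 / 15.7 percentage points. That is coarse, and a request does not count tablets taken.

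**What an opioid item would add.** If total doses were observed with the same CVs, the chance of a significant fall for true falls of 2.5 to 15% is 4-32% at CV 0.5 and 4-15% at CV 0.8. For a halved opioid count with an assumed CV of 1.5 or 2, power is 38% or 24%.

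**Baseline adjustment.** SE ratio = √(1−r²), which is 0.954 / 0.866 / 0.800 at baseline-outcome correlations r = 0.3 / 0.5 / 0.6. The 95% half-width is 1.984×SE×√(1−r²), as a percentage of the control mean:

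| | r = 0 | 0.3 | 0.5 | 0.6 |
|---|---|---|---|---|
| Half-width, CV 0.5 | 19.8 | 18.9 | 17.2 | 15.9 |
| Half-width, CV 0.8 | 31.7 | 30.3 | 27.5 | 25.4 |
| Power for a 20% difference, CV 0.5 | 51% | 55% | 63% | 70% |
| Power for a 20% difference, CV 0.8 | 24% | 25% | 30% | 34% |

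These correlations are generous for skewed counts. A simulation used negative binomial counts with extra zeros (15% tablet-type, 40% opioid-type), 80 or 100 patients, prior narcotic use of 10 or 25%, and 6,000 runs per setting with no arm effect. It gave SE ratios of 0.920-0.928 for tablet-type and 0.980-0.984 for opioid-type counts. Rejection rates with HC3 robust standard errors were 3.7-5.0% unadjusted and 3.5-4.8% adjusted, so type I error is not at issue. None of the SE figures applies to the 1-5 pain score.

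**The case against.** **The gap may not exist.** The questionnaire is not in the text, the section 20a list is not exclusive, and opioid prescribing is not stated. Harm needs opioids to be in use, the survey to omit them, and the video to shift their use. All of this stands: the finding is conditional, and that limits its weight.

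**The chart may fill it.** A reader might infer that opioid use goes unrecorded. The documents do not support that. Refill requests, visit notes (a two-week visit is routine) and telephone encounters may all show some opioid use. What remains is that none is stated to give a count of tablets taken.

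**The new item would rarely detect anything.** This stands, by the power figures above. Its value is in preventing a wrong interpretation.

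**Adjustment is optional, and no analysis is stated for any outcome.** Also fair. A reader might infer that the unadjusted comparison is biased or inflates false positives. With randomization it is neither, and the cost is modest precision. Naming the two covariates is still worthwhile, because they are the pre-operative counterparts of these outcomes and cost nothing further to collect.

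**Conclusion.** The point holds in conditional form and is minor. If opioids are used after surgery and the questionnaire does not ask about them, Tylenol and ibuprofen counts cannot carry a conclusion about total pain medication and can move against it. Under the assumed shares, a fall in total doses of 2.5-7.5% can go with a rise in the counts of 2.8-10.7%. If no opioids are used, there is no loss.

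The unused baseline data cost an SE gain of roughly 7-8% for tablet counts and 2% for sparse opioid counts, again under assumed inputs.

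A reader might extend this to the trial's main result or to all of hypothesis 2. The documents do not support that: satisfaction is primary, and neither it nor the compliance and recovery parts rest on these counts.

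**What to change.** 1. Add one survey item, *prescription opioid tablets taken since surgery (name, strength, number; 0 if none)*, or list it in section 20a if the questionnaire already has it. Report by arm opioid use (any, and number), Tylenol tablets, ibuprofen tablets and the proportion with a refill request, each as a difference with a 95% confidence interval. State that less pain medication use will not be concluded from the Tylenol and ibuprofen counts alone.

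   Do not add a rule that labels any mixture of rising and falling estimates a change in mix. With 50 per arm and independent estimates (assumed tablet CV 0.5-0.8, opioid CV 1.5-2, refill rate 5-20%), such a rule would apply that label to about 85-86% of trials with no effect. It would also apply it to 47-62% of trials with a true uniform 20% reduction.

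2. Pre-specify that two-week tablet counts are compared by linear regression on arm with robust standard errors, and the pain score by an ordinal model. Adjust both for pre-operative pain level and pre-operative narcotic use as charted before randomization. State that the expected gain is modest.

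Cost: one more two-week recall item in a survey of about 10 minutes, and a few sentences of analysis text. The baseline data are already planned for collection. The adjusted odds ratio for pain is a different quantity from the unadjusted one and should be labelled as such.

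### Pain medication use is described only as tablet counts without strength, an imperfect and possibly imprecise measure of the amount that Hypothesis 2 asks about

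*Combined protocol and SAP*

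**What the plan says.** The second research question in Section 12 asks whether greater understanding will lead to "less pain medication usage, less ambiguity and thus increased compliance with post-operative care instructions, and quicker recovery". The first of these is a question about amount.

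Section 20a (Procedures) lists the survey measures. For medication they are "Tylenol tablets used (over two weeks), Ibuprofen tablets used (over two weeks"), reported at about two weeks after surgery. No milligrams per tablet, total milligrams or fixed product is mentioned.

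Section 20a also draws on records: "Additional information will be collected from the patient's medical records (ie. office visit notes, telephone encounters, hospital laboratory results, pain medication refill requests"). The chart-review list in Section 20b has one analgesic item, narcotic use before the operation. Neither source is said to capture the strength of tablets taken after surgery.

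The measure is not primary. Section 20a states: "Our primary outcomes will be patient level of satisfaction with the education they received prior to surgery", scored on a Likert scale. The sample-size statement in Section 15 concerns post-operative experience in general, not tablet use.

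**The concern.** A tablet is not a fixed unit of drug if the product comes in more than one strength. Two patients with the same milligram intake can then report different counts, and two with the same count can have taken different amounts. Tablet counts are the main measure described for the medication part of Hypothesis 2.

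Two things could be at stake. The first is precision: variation in strength adds scatter unrelated to the amount taken, in a trial of 100 patients with no power calculation for this measure. The second is bias: which product a patient takes is settled after randomisation, so randomisation alone would not protect the comparison if the two formats of instruction led patients to different products. The first follows under stated assumptions. The second is only a possibility.

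**Working it through.** **The plan's own figure.** Section 15 states that "we determined that 100 subjects will be needed to predict a difference of improvement in patient's post-operative experience ranges 20% or greater". Alpha, power, base rate and standard deviation are not given, so 100 cannot be reproduced. With two-sided alpha 0.05 and 80% power, 75% versus 95% needs 98 in total and 50% versus 70% needs 186; a 20% difference in a mean needs 102 if the CV is 0.36. None of this is tied to tablet use.

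**Assumed inputs (not in the documents).** Acetaminophen tablets of 325, 500 or 650 mg; ibuprofen tablets of 200, 400, 600 or 800 mg; 50 patients per arm (the allocation ratio is not stated); two-sided alpha 0.05; no dropout.

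**Step 1: same intake, different counts.**
- 8,400 mg of ibuprofen is 42, 21, 14 or 10.5 tablets at 200, 400, 600 or 800 mg: a 4-fold range.
- 14,000 mg of acetaminophen is about 43, 28 or 21.5 tablets at 325, 500 or 650 mg: a 2-fold range.

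**Step 2: precision, with the same mix in both arms and milligram intake independent of strength.** Count = milligrams / strength, so

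CV²(count) = (1 + CV²(mg)) × (1 + CV²(1/strength)) − 1.

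For a 50:50 mix at strength ratio r, CV²(1/strength) = ((r − 1)/(r + 1))². With CV(mg) = 0.8, CV²(mg) = 0.64:

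| Mix | CV²(1/strength) | CV²(count) | Information kept |
|---|---|---|---|
| 325/500 mg | (175/825)² = 0.045 | 1.64 × 1.045 − 1 = 0.714 | 0.64/0.714 = 0.90 |
| 2:1 | 0.111 | 0.822 | 0.78 |
| 3:1 | 0.25 | 1.05 | 0.61 |
| 4:1 | 0.36 | 1.23 | 0.52 |

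At 3:1, 50 per arm behaves like 50 × 0.61, or about 30. Among the assumed strengths, acetaminophen spans at most 2:1, so the last two rows apply to ibuprofen only.

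**Step 3: power for a true 20% reduction, over a range of CV(mg).**

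| CV(mg) | Milligrams | Tablets, 325/500 mg mix | Tablets, 200/600 mg mix |
|---|---|---|---|
| 0.30 | 0.92 | 0.76 | 0.38 |
| 0.36 | 0.79 | 0.65 | 0.34 |
| 0.50 | 0.52 | 0.44 | 0.27 |
| 0.75 | 0.27 | 0.24 | 0.17 |

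At CV 0.8, the standard error in milligrams is 0.8 × √(2/50) = 0.16 of the mean. Power is then Φ(0.20/0.16 − 1.96) = Φ(−0.71), about 0.24. For tablets at 3:1 the CV is √1.05 = 1.02 and power is about 0.16.

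**Step 4: validity.** In simulations of a 200/600 mg mix common to both arms, type I error was 0.047 to 0.053, and a true 20% reduction appeared as a ratio of about 0.80. The comparison is noisier but not distorted.

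**Step 5: what a differing mix would do.** Take relative counts of 3 (200 mg) and 1 (600 mg) for equal milligrams. If 50% of one arm and 60% of the other used 600 mg, mean counts would be 0.5 × 3 + 0.5 × 1 = 2.0 and 0.4 × 3 + 0.6 × 1 = 1.8: a false 10% reduction, with simulated type I error of 0.08 to 0.12. These splits are hypothetical.

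**Step 6: the opposite assumption.** If patients take similar numbers of tablets whatever the strength, Step 2 does not apply. Fourteen tablets would be 14 × 200 = 2,800 mg for one patient and 14 × 600 = 8,400 mg for another, and the count would show no difference.

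**The case against.** Several objections are fair.

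- **The questionnaire was not available.** Section 20a is a short summary under a half-page limit, and the form may already ask for strength. This stands, and the fix is worded accordingly.
- **Varying strengths are an assumption.** This is one clinic and one physician group with same-day discharge. If patients mostly use one strength, little or nothing is lost. This stands.
- **The loss figures depend on intake being independent of strength.** If tablet number is independent of strength instead, the formula runs in reverse and milligrams are the noisier measure. This stands. But milligrams would still be the quantity Hypothesis 2 asks about, and counts would conceal real differences in it.
- **The wide ratios do not apply to both drugs.** For a 325/500 mg acetaminophen mix the loss is modest.

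A reader might infer that tablet counts cannot reliably answer Hypothesis 2. The documents do not support that. With a common mix the test is valid, and at a CV of 0.8 power for a 20% reduction is low even in milligrams (about 0.24), so strength is not the main limit on this question.

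A reader might also infer a spurious difference between arms. Section 17 says that "the patient will be randomized to receive the preoperative instructions verbally or via an instructional video", which describes two formats of the instructions, and nothing shows that they name different products. Bias remains a conditional possibility.

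**Conclusion.** The point holds as a modest, conditional improvement. The plan describes the amount of pain medication by a count whose unit is not fixed. If strengths vary and milligram intake does not depend on strength, counts keep about 90% of the information for a 325/500 mg acetaminophen mix, and about 78%, 61% or 52% at ratios of 2:1, 3:1 or 4:1 (CV 0.8, 50:50 mix; the last two for ibuprofen only). If tablet numbers are similar whatever the strength, the fault is instead that counts hide differences in amount. If one strength is used throughout, there is no loss. Validity is not in question unless the mix differs by arm, for which there is no evidence in the documents. The primary outcome is unaffected. The reason to act is that the investigators cannot tell which case applies unless they ask, and strength is unlikely to be recoverable long after the two-week survey.

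**What to change.** First check the questionnaire. Unless it already does so, add product and milligrams per tablet beside each count in the REDCap survey, allowing more than one strength per drug and an 'unknown' option. Use the chart value as a check for prescribed tablets only, since it could give the wrong strength for tablets bought over the counter. State that total milligrams of each drug over the two weeks will be compared between arms, with tablet counts shown as a supporting result.

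The cost is two or three extra fields, with no extra visits, and some strengths that are missing or misremembered. The change concerns measurement only and implies no dose or regimen.
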